1.3 STUDY CALENDAR

Assessments	Screening 28-day window up to Day 1 of treatment ¹	Day 1 of Every ODD Cycles (1, 3, 5...) +/- 5 days	Day 1 of every EVEN cycle Cycles (2, 4, 6...) +/- 5 days	END of Treatment Visit ²	Follow Up ³ (every 3M from EOT Visit
Informed Consent ⁴	X				
Inclusion/Exclusion Criteria	X				
Medical History/ Prior Treatment ⁵	X				
Concomitant medications	X	X	X	X	
Physical Exam	X	X	X	X	
Performance Status (ECOG or KPS)	X	X	X	X	
Vital signs/Weight/Height ⁶	X	X	X	X	
Drug Toxicity Assessment ⁷	X	X	X	X	
Baseline daily stool count	X				
ECG ⁸	X ⁹	EVERY 12 weeks (Pre- Cycle 5, 9, 13, ...)		X	
ECHO- 2D/MUGA	X				
Pregnancy test ¹⁰	X				
CBC with Differential ¹¹	X	X	X	X	
Chemistries ¹²	X	X	X	X	
PT/INR and PTT ¹³	X			X	
Urinalysis and UPC	X	X	X	X	
Thyroid Function Tests ¹⁴	X		X	X	
Amylase, Lipase	X	Every 12 weeks (Pre-Cycle 5, 9, 13...)		X	
Hepatitis B and C ¹⁵	X				
Tumor Imaging- CT Chest/Abdomen/Pelvis ¹⁶	X	Every 12 weeks (Pre- Cycle 5, 9, 13...)		X	
Brain MRI ¹⁷	X				
Pill Diary/Pill Count ¹⁸		X	X	X	
Research Blood ¹⁹ Phase II only	X	At week 7 (+/- 1 week) and progression			
Archival Tissue ²⁰ Phase II only	X				
Tissue Biopsy ²¹ Phase II Part 2 only	X	At week 7 (+/- 1 week) and progression			
Cabozantinib PO		Daily	Daily		
Pembrolizumab IV (30- minute infusion)		Day 1 of each Cycle			
Survival Status					X

¹ Routine laboratory tests for screening should be performed within 14 days of cycle 1.

² End of treatment visit will be completed 30 days (+/- 7 days) from date of last dose of study drug or before another treatment starts whichever occurs first.

³ Subjects will be followed for survival and progression post treatment every 3 months x 2 years, every 6 months x 3 years and yearly until death. Every 3 months from EOT visit.

⁴ Written consent must be obtained prior to performing any protocol specific procedure. Results of a test performed as part of routine clinical management are acceptable in –lieu of a screening test if performed within the specified time frame. (e.g., within 28 days period to Cycle 1 Day 1.)

⁵ Report complete medication history for 30 days prior to the screening visit. Medical history should include history of treatment for the primary diagnosis, including prior systemic, radiation treatment and surgical treatment and best response to prior systemic treatments. Date of last prior cancer treatment must be documented.

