- Interruption of cabozantinib treatment for AEs may occur at any time per investigator discretion. If treatment is interrupted due to AEs for more than 6 weeks, patient will be taken off study unless the investigator deems there to be previous or ongoing clinical benefit.
- Dose interruptions for reason(s) other than AEs (eg, surgical procedures) can be longer than 6 weeks but require Sponsor approval. The acceptable length of interruption will depend on agreement between investigator and the Sponsor.
- Dose interruptions may occur in 2 ways:
 - Within a cycle:** If dosing interruption and/or dose reduction occurs between Day 1 and Day 21 of a cycle (including protocol-specified windows), the cycle proceeds as planned.
 - Prior to the initiation of a new cycle:** If the investigator decides on day 1 of a new cycle that dose interruption should occur, that cycle may be delayed. When the investigator decides that dosing should resume, the day that the patient restarts drug will be day 1 of that new cycle. Re-escalation to any previous dose may be allowed at the discretion of the investigator no sooner than 2 weeks beyond resolution of AEs that led to the dose reduction. Dose re-escalation is not allowed for a previous dose reduction triggered by Grade 4 hematologic toxicities or by Grade 4 AEs affecting major organs (eg, central nervous system, cardiac, hepatic, renal).

Table 4: Dose Modifications of Cabozantinib for Treatment Related AEs

CTCAE v4.0	Recommended Guideline for Management
Grade 1 AEs	Supportive care as indicated. Continue cabozantinib at the current dose level if AE is manageable and tolerable.
Grade 2 AEs which are tolerable and are easily managed	Continue cabozantinib at the current dose level with supportive care.
Grade 2 AEs which are intolerable and cannot be adequately managed	At the discretion of the investigator, cabozantinib should be dose reduced or interrupted. Note: It is recommended that dose holds be as brief as possible.
Grade 3 AEs (except clinically non-relevant laboratory abnormalities)	Cabozantinib should be interrupted unless the toxicity can be easily managed with a dose reduction and optimal medical care. Note: It is recommended that dose holds be as brief as possible
Grade 4 AEs (except clinically non-relevant laboratory abnormalities)	Subjects should have cabozantinib interrupted immediately.

Discontinue cabozantinib unless the following criteria are met:

<

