- Subject is deriving clear clinical benefit as determined by the investigator.<
- Toxicity can be managed with a dose reduction following recovery to Grade 1 (or baseline) and optimal medical care.

6.2 WARNINGS, PRECAUTIONS, AND GUIDELINES FOR MANAGEMENT OF ADVERSE EVENTS:

THE FOLLOWING ARE TO BE CONSIDERED AS GENERAL GUIDELINES.
TREATING PROVIDER WILL MANAGE AS DEEMED CLINICALLY INDICATED.

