Grade 1	Cabozantinib treatment may be continued at the current dose if PPE is clinically insignificant and tolerable. Otherwise, cabozantinib should be reduced to the next lower dose level. Start urea 20% cream twice daily and clobetasol 0.05% cream once daily. Reassess at least weekly; if PPE worsens at any time or does not improve after 2 weeks, proceed to the intervention guidelines for Grade 2.
Grade 2	Cabozantinib treatment may be continued if PPE is tolerated. Cabozantinib should be dose reduced or interrupted if PPE is intolerable. Continue urea 20% cream twice daily and clobetasol 0.05% cream once daily and add analgesics (eg, NSAIDs/GABA agonists) for pain control if needed. Reassess at least weekly; if PPE does not improve within 2 weeks or worsens or affects self-care, proceed to the intervention guidelines for Grade 3.
Grade 3	Interrupt cabozantinib treatment until severity decreases to Grade 1 or 0. Continue treatment of skin reaction with clobetasol 0.05% cream twice daily and analgesics. Resume cabozantinib at reduced dose if PPE recovers to Grade 0 or 1. Discontinue subject from study if intolerable PPE recurs after dose reduction or does not improve within 6 weeks.

CTCAE, Common Terminology Criteria for Adverse Events; GABA, gamma-amino butyric acid; NSAID, non-steroidal anti-inflammatory drug; PPE, palmar-plantar erythrodysesthesia.

HYPERTENSION

Hypertension has been reported in subjects treated with cabozantinib. Blood pressure should preferably be monitored in a constant position visit to visit in a relaxed setting. Treatment guidelines for hypertension deemed related to cabozantinib are presented below.

Grade 2 Hypertension (Systolic 140-159, Diastolic 90-99) Antihypertensive Therapy:
Continue Cabozantinib and consider the following:

Step 1) Initiate LA dihydropyridine calcium-channel blocker treatment (such as amlodipine) and if needed, after 24-48 hours of treatment, increase dose in stepwise fashion every 24-48 hours until BP is controlled or at the maximum dose of therapy.

Step 2) If BP still not controlled, consider adding another antihypertensive agent, a selective beta blocker, angiotensin converting enzyme inhibitors, angiotensin II receptor blockers, alpha beta blocker; increase dose of this drug as described in step 1.

Step 3) If BP still not controlled, consider adding a 3rd drug from the list of antihypertensives in step 2; increase dose of this drug as described in step 1.

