7.2 PARTICIPANT DISCONTINUATION/WITHDRAWAL FROM THE STUDY

Patients may withdraw from the study at any time. Patients who discontinue early should return within 30 days (+/- 7 days) of the last dose of the study drugs for a follow-up evaluation. Any assessments listed for the final visit in Table will be performed at that time.

In addition, any of the following conditions require the withdrawal of the subject from study treatment:

- An AE or intercurrent illness that in the opinion of the investigator warrants the subject's withdrawal from treatment
 - The investigator believes it is not in the best interest of the subject to continue on study
- Necessity for treatment with other investigational drug or other anticancer medications prohibited by protocol
- Noncompliance with the protocol schedule
- Participation in another clinical study using anticancer agent(s)
- Request by regulatory agencies for termination of treatment of an individual subject or all subjects under this protocol
- Sexually active subjects who refuse to use medically accepted barrier methods of contraception (eg, male condom, female condom) during the course of the study and for 3 months following discontinuation of study treatment
- Women who become pregnant or are breast feeding
- Inability to tolerate cabozantinib
- Cabozantinib treatment delays > 6 weeks unless the subject was unequivocally benefitting from cabozantinib treatment
- Progressive disease (PD) as determined by the investigator. However, patients who continue to derive clinical benefit from cabozantinib and pembrolizumab as judged by the investigator may continue therapy despite radiographic progression of the disease.

The reason for study treatment discontinuation will be documented. For subjects who discontinue or are withdrawn from study treatment, every effort must be made to undertake protocol-specified follow-up procedures and end-of-treatment assessments, if possible, unless consent to participate in the study is also withdrawn.

If a subject fails to return for the protocol-defined visits, an effort must be made to determine the reason. If the subject cannot be reached by telephone, at the minimum a registered letter

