should be sent to the subject (or the subject's legal guardian) requesting contact with the clinic. If a subject is discontinued from study treatment because of an AE considered to be related to study treatment and the event is ongoing 30 days after the last dose of study treatment, the event must be followed until resolution or determination by the investigator that the event has become stable or irreversible.

If a subject withdraws consent to participate in the study, the reason for withdrawal will be documented, no further study procedures or assessments will be performed, and no further study data will be collected for this subject, other than the determination of survival status from public records such as government vital statistics or obituaries.

Patients that withdraw from study treatment (but not their consent for follow-up) for reasons other than progression will continue to have scans per study calendar until PD is noted.

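### For a cabozantinib hold of more than 6 weeks due to an AE, 6.1.2.3 takes the patient off study, whereas 7.2 withdraws only study treatment, continues scans and applies a different benefit exception

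*Combined protocol and SAP*

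**What the plan says.** Section 6.1.2.3 (Dose Modification and Interruption) sets this rule for holds caused by toxicity: "If treatment is interrupted due to AEs for more than 6 weeks, patient will be taken off study". The sentence goes on with an exception: "unless the investigator deems there to be previous or ongoing clinical benefit".

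Section 7.2 (Participant Discontinuation/Withdrawal from the Study) opens its list with the words "any of the following conditions require the withdrawal of the subject from study treatment". One entry reads "Cabozantinib treatment delays > 6 weeks unless the subject was unequivocally benefitting from cabozantinib treatment". The section closes by saying that patients who leave study treatment, but keep their consent to follow-up, "for reasons other than progression will continue to have scans per study calendar until PD is noted".

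Section 6.2.1, Table 6, has similar wording for Grade 3 palmar-plantar erythrodysesthesia (PPE): "Discontinue subject from study if intolerable PPE recurs after dose reduction or does not improve within 6 weeks". That table stands under the label at the start of 6.2, "THE FOLLOWING ARE TO BE CONSIDERED AS GENERAL GUIDELINES", which leaves management to the treating provider. Section 6.1.2.3 comes before that label and is not covered by it.

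**The concern.** A patient whose cabozantinib is held for more than 6 weeks because of an AE meets both rules, and the rules give different instructions. One removes the patient from the study. The other stops treatment and continues imaging. They also except different patients. No sentence in the protocol gives one section precedence.

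What is at stake is tumor follow-up in patients who stop for toxicity. The primary endpoint in 8.1 is the best confirmed response at any time during the study, and PFS is censored at the last tumor assessment. Both depend on scans being taken after treatment ends. A site that follows 6.1.2.3 to the letter would stop those scans, and a site that follows 7.2 would not.

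**Working it through.** The check is a comparison of text; the plan gives no figure on this point.

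**The rules side by side**

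| | 6.1.2.3 | 7.2 |
|---|---|---|
| Trigger | Hold over 6 weeks due to an AE | Cabozantinib delay over 6 weeks, any reason |
| Consequence | Off study | Off study treatment; scans continue to progression if consent to follow-up stands |
| Exception | Past or present clinical benefit, as the investigator judges | Unequivocal benefit from cabozantinib |

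**Overlap.** The 7.2 trigger is the wider one. The two rules meet on AE holds, and the point is confined to those.

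**Three patients, each with an AE hold of more than 6 weeks**

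1. *No benefit.* Under 6.1.2.3 the patient leaves the study. Under 7.2 the patient leaves treatment and is scanned until progression. The difference is the imaging.
2. *Some benefit, but not unequivocal.* 6.1.2.3 excepts this patient, who may stay on. 7.2 requires withdrawal from treatment. A site that uses the latitude in 6.1.2.3 departs from 7.2, and a site that applies 7.2 leaves the 6.1.2.3 exception without effect. This conflict remains even if off study is read as off treatment.
3. *Unequivocal benefit from cabozantinib.* Both sections except the patient. There is no conflict.

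**What the literal reading would do to the endpoints (patient 1)**

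- *Response.* Under 9.4.2 a patient who has not met the response criteria by the cutoff counts as a non-responder. A response that would first have appeared on a later scheduled scan is missed if that scan is not taken.
- *PFS.* Sections 8.1 and 9.4.3 censor at the last radiographic assessment. If scans stop, that date is the last scan before the patient left.
- *Other follow-up.* Study calendar footnote 3 and 8.3.4.2 follow patients for survival and progression every 3 months at first. Section 8.3.4.2 does this by telephone, correspondence with treating physicians and death records. Neither place requires a CT, so neither replaces the scans in 7.2.

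**Scan interval.** The calendar ties CT to the visits before cycles 5, 9 and 13. A cycle is 21 days, so the visit before cycle 5 falls at 4 x 21 = 84 days (week 12) and the visit before cycle 9 at 8 x 21 = 168 days (week 24). A patient off treatment has no cycles, so the interval has to be stated in weeks from first dose. Every 12 weeks is the same schedule.

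**Design figures.** These are not in question. Take 14 then 30 patients, continue with 6 or more responses, and reject with 21 or more of 44. The sum over x = 6 to 14 of P(X1 = x) x P(X2 >= 21 - x), with X1 ~ Bin(14, p) and X2 ~ Bin(30, p), is 0.0458 at p = 0.35 and 0.8001 at p = 0.55. This agrees with the stated alpha of 0.05 and power of 80%. The wording conflict does not change these values.

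**The case against.** The strongest reply is that context settles the meaning. Section 7.2 is the section devoted to withdrawal, names the 6-week delay as a reason to stop treatment, and says that scans go on. Its own list uses *on study* loosely: an investigator's view that the patient should not continue on study is listed as a reason to withdraw treatment. The text that expressly stops assessments is the paragraph on withdrawal of consent, and 6.1.2.3 does not mention imaging at all. Table 6 is guidance only.

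Most of this stands. Off study in 6.1.2.3 was probably meant as off study treatment, and the loss of scans follows only from a literal reading. But the protocol does not define the term that way, 6.1.2.3 is written as an instruction outside the general-guidelines label, and Table 6 has similar wording. The argument also leaves the mismatch between the two exceptions untouched.

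A reader might also infer that responses already seen would go unconfirmed. The documents do not support that. Section 8.1 calls for a second scan in any patient with a CR or PR, and a documented response could itself bring the patient within the 6.1.2.3 exception. What is exposed is the response that has not yet appeared when the patient leaves.

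**Conclusion.** The conflict is real, in consequence and in exception, and no precedence is stated. It is a minor point. The effect on response and PFS follow-up assumes a site that reads 6.1.2.3 literally, and a patient without recognized benefit who would later have responded or progressed on a scheduled scan.

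No size is claimed. The documents give no rate of AE holds beyond 6 weeks. The nearest figure, dose reductions in 48.7% of patients in the 100 mg phase 2 trial (2.2.2.2), concerns a different event at a higher dose.

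Three stronger conclusions that a reader might draw are not supported:

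- *That ORR is biased by a given amount, or that power is lost.* Any such figure would need an assumed number of affected patients, for which the documents give no basis.
- *That this wording removes patients from the efficacy analysis.* The exclusion of patients with no post-baseline scan comes from the mITT definition in 9.3, which is a separate matter.
- *That the end-of-treatment CT falls due too early because of this conflict.* The calendar says "End of treatment visit will be completed 30 days (+/- 7 days) from date of last dose of study drug", so the window closes at 30 + 7 = 37 days, while the hold rule acts after 6 x 7 = 42 days. If both drugs are held, that gap of at least 5 days arises under either section, and a late scan still counts as post-baseline imaging.

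**What to change.** 1. In 6.1.2.3, replace the off-study wording with: *withdrawn from study treatment; scans continue every 12 weeks from first dose until PD, per 7.2*.
2. In Table 6, Grade 3, replace the instruction to discontinue the subject from the study with: *withdraw subject from study treatment (see 7.2)*. Wording that stops cabozantinib alone should be avoided. It would imply that pembrolizumab may continue, whereas 7.2 lists inability to tolerate cabozantinib as a reason to withdraw study treatment.
3. Use one benefit exception in both 6.1.2.3 and 7.2. Which one is a clinical choice for the sponsor.

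The cost is a wording amendment to 6.1.2.3, Table 6 and, depending on the exception chosen, 7.2. No scans are added beyond those that 7.2 already requires.

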6.2.1 CABOZANTINIB

The side effect profile of cabozantinib includes GI symptoms (such as nausea, vomiting, and diarrhea), fatigue/asthenia, anorexia, weight loss, skin rash including PPE syndrome, mucosal inflammation/stomatitis, and hypertension. Subjects may also experience medically important but less frequent adverse events including arterial and venous thrombotic events such as deep vein thrombosis (DVT), pulmonary embolism (PE), transient ischemic attack, and myocardial infarction; severe hemorrhagic events, proteinuria, wound healing complications, GI perforation, intraabdominal and pelvic abscess, GI and non-GI fistulae formation, osteonecrosis, and reversible posterior leukoencephalopathy syndrome (RPLS).

Common laboratory abnormalities reported as AEs include ALT increased, AST increased, TSH increased, hypokalemia, hypomagnesemia, hypophosphatemia, hypocalcemia, lipase increased, and thrombocytopenia.

Please refer to the Investigator's Brochure for additional details.

As with all investigational products, unknown AEs may occur. Subjects should be monitored closely for all AEs. The predicted effective plasma half-life of cabozantinib is 99 hours.

Thus, when initiating therapy with cabozantinib, it will take most subjects 2-3 weeks to reach steady state. If AEs attributable to cabozantinib occur within the initial 3-week period of dosing, early intervention with dose modifications may be justified for AEs that, if worsened, could potentially be dangerous or debilitating, since without a dose adjustment, systemic exposure of cabozantinib might be expected to increase after the onset of the AE.

Cabozantinib should be discontinued for the following adverse events: visceral perforation or fistula formation, severe hemorrhage, serious arterial thromboembolic events (e.g MI, cerebral infarction), nephrotic syndrome, malignant hypertension, hypertensive crisis, persistent uncontrolled hypertension despite optimal medical management, osteonecrosis of the jaw (ONJ), and RPLS.

Management of gastrointestinal disorders, hepatobiliary disorders, hematological disorders, fatigue, anorexia, weight loss, skin disorders, hypertension, thromboembolic events,

proteinuria, QTc prolongation, hypophosphatemia and thyroid function disorders are presented in this section as these have been observed in previous studies with cabozantinib or represent common class effect toxicity. In addition, guidelines to minimize the risk for potential serious adverse events (SAEs) such as GI perforation, GI and non-GI fistula formation, hemorrhagic events, and osteonecrosis of the jaw (ONJ) are provided in this section.

Please refer to the Investigator's Brochure for additional practice guidelines and management recommendations for side effects potentially related to cabozantinib treatment; available information on potential risk of congenital, familial and genetic disorders; and guidelines on management of overdose of cabozantinib study treatment.

GASTROINTESTINAL DISORDERS

The most common GI AEs reported in clinical studies with cabozantinib are diarrhea, oral pain, dyspepsia, stomatitis, and dysphagia.

DIARRHEA

Subjects should be instructed to notify their physician immediately at the first signs of poorly formed or loose stool or an increased frequency of bowel movements. Administration of antidiarrheal/ antimotility agents is recommended at the first sign of diarrhea as initial management. Some subjects may require concomitant treatment with more than one antidiarrheal agent. When therapy with antidiarrheal agents does not control the diarrhea to tolerable levels, study treatment should be temporarily interrupted or dose reduced according to the table 5. When the diarrhea is controlled, retreatment with study treatment may be acceptable per investigator decision. In addition, general supportive measures should be implemented including continuous oral hydration, monitoring for and correction of fluid and electrolyte abnormalities, small frequent meals, and stopping lactose-containing products, high fat meals, and alcohol.

Table 5: Guidelines for management of Treatment-Emergent Diarrhea

Status	Management
Tolerable Grade 1-2 (duration < 48 h)	
Continue with study treatment and consider dose reductionInitiate treatment with an antidiarrheal agent (eg, loperamide 4 mg followed by 2 mg after each episode of diarrhea [maximum: 16 mg loperamide per day])Dietary modifications (eg, small lactose-free meals, bananas and rice)

	
 • Intake of isotonic fluids (1-1.5 L/day) • Re-assess after 24 hours: 
 Diarrhea resolving to baseline bowel habits: gradually add solid foods and discontinue or decrease antidiarrheal treatment after 12 h diarrhea-free interval Diarrhea not resolving: Continue/resume antidiarrheal treatment
Intolerable Grade 2, Grade 2 > 48 h, or \geq Grade 3	
 • Interrupt study treatment • Ask subject to attend clinic • Rule out infection (eg, stool sample for culture): Administer antibiotics as needed (eg, if fever or Grade 3-4 neutropenia persists > 24 h) • Administer fluids (1-1.5 L/day orally or IV, as appropriate) for hydration or to correct electrolyte abnormalities • For Grade 3-4 or complicated lower grade diarrhea consider hospitalization and IV hydration • Re-assess after 24 h 
 -- Diarrhea resolving to baseline bowel habits or Grade \leq 1: consider restarting study treatment at reduced dose -- Diarrhea not resolving: Start and/or continue antidiarrheal treatment (eg, loperamide 4 mg followed by 2 mg after each episode of diarrhea [maximum: 16 mg loperamide per day]) 
Consider starting second line antidiarrheal or referral to gastroenterologist

NAUSEA AND VOMITING

Antiemetic agents are recommended as clinically appropriate at the first sign of nausea and vomiting or as prophylaxis to prevent emesis, along with supportive care according to clinical practice guidelines. The 5-HT3 receptor antagonists are recommended over chronic use of NK-1 receptor antagonists and dexamethasone (NK-1 receptor antagonists can induce or inhibit CYP3A4, and glucocorticoids induce CYP3A4 and thus could lower cabozantinib exposure. Caution is also recommended with the use of nabilone, which is a weak inhibitor of CYP3A4. Medications should be assessed for potential drug interactions (refer to the current version of the Investigator's Brochure for further details).

STOMATITIS AND MUCOSITIS

Preventive measures may include a comprehensive oral examination to identify and treat any potential risk for complications before study treatment is initiated. Appropriate correction of local factors should be instituted as indicated, such as modification of ill-fitting dentures and appropriate care of gingivitis. During treatment with cabozantinib good oral hygiene and standard local treatments such as non-traumatic and non-irritating cleansing and oral rinses (eg, with a weak solution of salt and baking soda) should be maintained. The oral cavity should be rinsed and wiped after meals, and dentures should be cleaned and brushed often to remove plaque. Lips should be kept moisturized with lip balm. The use of lipstick, lip-gloss, and Vaseline should be avoided. Local treatment should be instituted at the earliest onset of symptoms. Obtain bacterial/viral culture if oral infection is suspected and treat infection as indicated as clinically indicated. When stomatitis interferes with adequate nutrition and local therapy is not adequately effective, dose reduction or temporary withholding of cabozantinib should be considered.

HEPATOBILIARY DISORDERS

Cabozantinib is not recommended for use in patients with moderate or severe hepatic impairment, as safety and efficacy have not been established.

Elevations of ALT, AST, and bilirubin have been observed during treatment with cabozantinib. It is recommended that subjects with elevation of ALT, AST, and/or bilirubin have more frequent laboratory monitoring of these parameters. If possible, hepatotoxic concomitant medications should be discontinued in subjects who develop increased values of ALT, AST, or bilirubin.

1. For subjects who enter the trial with grade 1 ALT, AST or total bilirubin who experience a grade increase, consider having study treatment interrupted and/or dose reduced as outlined in Table 4 if hepatotoxicity is considered to be drug related.
2. For subjects with elevations of AST/ALT up to $5 \times$ ULN at baseline (such as in the presence of liver metastases), dose modifications and interruption are not required if there are no progressive drug related changes in the aminotransferases (more than a doubling on serial LFT testing) and if there are no progressive drug-related elevations in serum total bilirubin concentration (more than a doubling on serial LFT testing if baseline value is >1.5 ULN) or coagulation factors. Cabozantinib treatment should be interrupted when drug-related transaminase increases are accompanied by progressive drug-related elevations of total bilirubin, and/or elevations of coagulation tests (eg, International Normalized Ratio [INR]). More frequent monitoring of transaminases should be considered and study treatment should be held until the etiology of the abnormalities is determined and these abnormalities are corrected or stabilize at clinically acceptable levels. If hepatic toxicity resolves during a temporary hold and was deemed related to study treatment, then study treatment may be restarted at a reduced dose.
3. Study treatment should be discontinued if hepatic dysfunction is not reversible despite temporary interruption of study treatment. Elevations $>3 \times$ ULN of ALT or AST concurrent with $>2 \times$ ULN total bilirubin without other explanation can indicate drug-induced liver injury and drug should be permanently discontinued.

Evaluation of subjects with elevated transaminases or total bilirubin should be individualized and guided by the presence of specific risk factors such as illnesses which affect liver function (eg, infectious and non-infectious causes of hepatitis, liver cirrhosis, thrombosis of portal or hepatic vein), concomitant hepatotoxic medication, alcohol consumption, and cancer related causes. AEs which are based on hepatic dysfunction should be managed according to locally accepted clinical practice, including monitoring of appropriate laboratory functions.

HEMATOLOGIC DISORDERS

Hematological toxicities (ie, neutropenia and thrombocytopenia) and associated complications have been observed after administration of cabozantinib and may be managed with dose interruptions and/or dose reductions. Use of granulocyte colony-stimulating factor support for neutrophil recovery is allowed per investigator discretion and in accordance with accepted guidelines after the first incidence of clinically relevant cytopenia.

Subjects with hematologic toxicities may require additional or more frequent laboratory tests according to institutional guidelines. Results of such tests are to be forwarded to the local laboratory data management vendor.

Febrile neutropenia or evidence of infection associated with neutropenia must be assessed immediately and treated appropriately and in a timely manner according to institutional guidelines.

Dose reductions or dose interruptions for anemia are not mandated but can be applied as clinically indicated. Supportive care such as red blood cell transfusions may be managed according to institutional guidelines.

FATIGUE

Fatigue has been reported during treatment with cabozantinib. Common causes of fatigue such as anemia, deconditioning, emotional distress (depression and/or anxiety), nutrition, sleep disturbance, and hypothyroidism should be ruled out and/or these causes treated according to standard of care. Individual non-pharmacological and/or pharmacologic interventions directed to the contributing and treatable factors should be given. Pharmacological management with psychostimulants such as methylphenidate should be considered after disease specific morbidities have been excluded.

Note: Chronic use of modafinil should be avoided because of its potential to reduce cabozantinib exposure.

Dose reduction of study treatment should be considered when general or pharmacological measures have not been successful in reducing symptoms. Dose interruption may be considered for Grade ≥ 3 fatigue despite optimal management, at the investigator's discretion.

ANOREXIA AND WEIGHT LOSS

Anorexia and weight loss should be managed according to local standard of care including nutritional support. Pharmacologic therapy should be considered for appetite enhancement. Should these interventions prove ineffective, dose hold and reductions may be considered for
Protocol_V5.1_16Jul2024

Grade ≥ 3 anorexia or weight loss. If anorexia and/or weight loss do not recur after a dose reduction, dose of cabozantinib may be re-escalated to the previous dose.

SKIN DISORDERS

WOUND HEALING AND SURGERY

Cabozantinib has the potential to cause wound healing complications and wound dehiscence which may occur even long after a wound has been considered healed. Therefore, surgical and traumatic wounds must have completely healed prior to starting cabozantinib treatment and be monitored for wound dehiscence or wound infection while the subject is being treated with cabozantinib. If clinically possible, Treatment with cabozantinib should be stopped at least 28 days prior to scheduled surgery. The decision to resume treatment with cabozantinib after surgery should be based on clinical judgment of adequate wound healing.

PALMAR-PLANTAR ERYTHRODYSESTHESIA SYNDROME

PPES, also known as hand-foot syndrome, skin rash (including blisters, erythematous rash, macular rash, skin exfoliation, dermatitis acneiform, and papular rash), pruritus, dry skin, erythema, pigmentary changes, and alopecia have been reported in cabozantinib-treated subjects. All subjects on study should be advised on prophylactic skin care. This includes the use of emollients, removal of calluses, avoidance of exposure of hands and feet to hot water leading to vasodilation, protection of pressure-sensitive areas of hands and feet, and use of thick cotton gloves and socks to prevent injury and to keep the palms and soles dry. Subjects with skin disorders should be carefully monitored for signs of infection (eg, abscess, cellulitis, or impetigo).

Early manifestations of hand-foot syndrome include tingling, numbness, mild hyperkeratosis and painful, symmetrical red and swollen areas on the palms and soles. The lateral sides of the fingers or peri-ungual zones may also be affected. Adequate interventions are required to prevent worsening of skin symptoms such as blisters, desquamations, ulcerations, or necrosis of affected areas. Aggressive management of symptoms is recommended, including early dermatology referral. Treatment guidelines for PPES related to study treatment are presented in Table 6.

In the case of study treatment-related skin changes (eg, rash, hand-foot syndrome), the investigator may request that additional assessments be conducted with the subject's consent. These assessments may include digital photographs of the skin changes and/or a biopsy of the affected skin and may be repeated until the skin changes resolve.

Table 6: Management of Treatment-emergent PPE Syndrome

CTCAE v.4.0	Action to be taken
Grade 1	Cabozantinib treatment may be continued at the current dose if PPE is clinically insignificant and tolerable. Otherwise, cabozantinib should be reduced to the next lower dose level. Start urea 20% cream twice daily and clobetasol 0.05% cream once daily. Reassess at least weekly; if PPE worsens at any time or does not improve after 2 weeks, proceed to the intervention guidelines for Grade 2.
Grade 2	Cabozantinib treatment may be continued if PPE is tolerated. Cabozantinib should be dose reduced or interrupted if PPE is intolerable. Continue urea 20% cream twice daily and clobetasol 0.05% cream once daily and add analgesics (eg, NSAIDs/GABA agonists) for pain control if needed. Reassess at least weekly; if PPE does not improve within 2 weeks or worsens or affects self-care, proceed to the intervention guidelines for Grade 3.
Grade 3	Interrupt cabozantinib treatment until severity decreases to Grade 1 or 0. Continue treatment of skin reaction with clobetasol 0.05% cream twice daily and analgesics. Resume cabozantinib at reduced dose if PPE recovers to Grade 0 or 1. Discontinue subject from study if intolerable PPE recurs after dose reduction or does not improve within 6 weeks.

CTCAE, Common Terminology Criteria for Adverse Events; GABA, gamma-amino butyric acid; NSAID, non-steroidal anti-inflammatory drug; PPE, palmar-plantar erythrodysesthesia.

HYPERTENSION

Hypertension has been reported in subjects treated with cabozantinib. Blood pressure should preferably be monitored in a constant position visit to visit in a relaxed setting. Treatment guidelines for hypertension deemed related to cabozantinib are presented below.

Grade 2 Hypertension (Systolic 140-159, Diastolic 90-99) Antihypertensive Therapy:
Continue Cabozantinib and consider the following:

Step 1) Initiate LA dihydropyridine calcium-channel blocker treatment (such as amlodipine) and if needed, after 24-48 hours of treatment, increase dose in stepwise fashion every 24-48 hours until BP is controlled or at the maximum dose of therapy.

Step 2) If BP still not controlled, consider adding another antihypertensive agent, a selective beta blocker, angiotensin converting enzyme inhibitors, angiotensin II receptor blockers, alpha beta blocker; increase dose of this drug as described in step 1.

Step 3) If BP still not controlled, consider adding a 3rd drug from the list of antihypertensives in step 2; increase dose of this drug as described in step 1.

Step 4) If BP still not controlled, consider either 1 dose reduction of cabozantinib or stopping cabozantinib.

NOTE: Stopping or reducing the dose of cabozantinib is expected to cause a decrease in BP. The treating physician should monitor the patient for hypotension and adjust the number and dose of antihypertensive medication(s) accordingly.

Grade 3 Hypertension (Systolic ≥ 160 Diastolic ≥ 100), hold cabozantinib until systolic BP ≤ 159 and diastolic BP ≤ 99 .

Antihypertensive Therapy: BP management is identical to that for grade 2 (see steps 1-4 above) with 2 major exceptions:

- 1) If systolic BP > 180 or diastolic BP > 110 and the patient is symptomatic:** consider inpatient hospitalization and management as clinically indicated.
- 2) If systolic BP > 180 or diastolic BP > 110 and the patient is asymptomatic,** 2 new antihypertensives must be given together in step 1 (and dose escalated appropriately as in step 1).

NOTE: Stopping or reducing the dose of cabozantinib is expected to cause a decrease in BP. The treating physician should monitor the patient for hypotension and adjust the number and dose of antihypertensive medication(s) accordingly.

Dose Modification: HOLD cabozantinib until systolic BP < 159 and diastolic BP < 99 . In most circumstances, if BP cannot be controlled after an optimal trial of antihypertensive medications, consider either 1 dose reduction of cabozantinib or stopping cabozantinib.

HOWEVER, if the patient requires hospitalization for management of symptomatic systolic BP > 180 or diastolic BP > 110 , permanently discontinue cabozantinib or if BP is controlled, re-start cabozantinib at one lower dose level after consultation with the Study Chair.

Grade 4 Hypertension (life-threatening consequences of hypertension)

Antihypertensive Therapy: Optimal management in inpatient setting. Recommend ICU support and IV medication. STOP cabozantinib and notify hospital staff that stopping cabozantinib may result in a decrease in BP.

Dose Modification: Permanently discontinue cabozantinib or if BP is controlled, re-start cabozantinib at 1 lower dose level after consultation with the Study Chair.

THROMBOEMBOLIC EVENTS

